## **2. Protocol**

Patients who have been interviewed, examined, and a plan has been made by the treating physicians in the Female Pelvic Medicine & Reconstructive Surgery practice will be invited to participate at the end of the visit if the patient and physician mutually agree that PFPT is the treatment modality to pursue.

If she agrees to participate, she will be consented and randomized. If she is randomized to standard counseling, she will be given the standard handout to read. If she is randomized to the intervention, she will be both given the standard handout and then view the 4-minute educational video on a clinic iPad.

At the conclusion of the counseling, patients will be asked if they have any additional questions, and these will be recorded and answered. The patient will also fill out a visual analog scale about how informed she feels. (See appendix 4.3 & 4.4)

**Follow-up:** Patient chart will be monitored following enrollment in the study to measure time to PFPT attendance and PFPT compliance (See appendix 4.5).

## **2.1. Eligibility criteria**

### **Inclusion criteria**

Patients who have prescribed PFPT by a treating physician in the Female Pelvic Medicine & Reconstructive Surgery practice

### **Exclusion criteria**

Patients < 18 years old

## **2.2. Consent Process**

Patients will be identified when they present to the Loyola Urogynecology out-patient clinic for management of their pessary. Consent form will be read to them describing the nature of the trial and potential associated risks and benefits. They will be informed that neither participation nor refusal will influence the care received at either Loyola University Medical Center. A copy of the consent form will be given to them.

Participation is completely voluntary and they may discontinue participation in the study at any time.

## **2.3. Trial Design**

Randomized controlled clinical trial

## **2.4. Randomization**

Block randomization strategy will be developed based on a 1:1 allocation of patients in the intervention and control groups. The randomization procedure will take place after informed consent is completed and eligibility status is determined.

## **2.5. Confidentiality**

Following HIPPA guidelines, patient identifiable data will be coded to protect each patient's identity. A unique identification number will be assigned to designate each subject, and all identification numbers identifying information will be removed from the database and stored separately on a secure password-protected network drive in the office of the PI.

Here is an overview of the security of the infrastructure:

### Physical

- Servers kept in locked cage
- Entry requires a passcard and biometric recognition
- Digital surveillance equipment
- Controls for temperature, humidity and smoke/fire detection
- Staffed 24/7

### Network

- Multiple independent connections to Tier 1 Internet access providers
- Fully redundant OC-48 SONET Rings
- Uptime monitored every 5 minutes, with escalation to SurveyMonkey staff
- Firewall restricts access to all ports except 80 (http) and 443 (https)
- QualysGuard network security audits performed quarterly

### Hardware

- Servers have redundant internal power supplies
- Data is on RAID 10, operating system on RAID 1
- Servers are mirrored and can failover in less than one hour

### Software

- Code in ASP, running on SQL Server 2000 and Windows 2000 Server
- Latest patches applied to all operating system and application files
- Data backed up every hour internally
- Data backed up every night to centralized backup system, with offsite backups in event of catastrophe

## **2.6. Statistical analysis**

Binary logistic regression will be used to compare the odds of PFPT initiation, PFPT discharge, completion of half of the recommended visits, and having any further questions after counseling between those assigned to the enhanced versus standard counseling groups. In these models, expected frequencies will be monitored and exact logistic regression models will be used when these values are sparse. We will also

stratify the comparison of PFPT initiation by participants' primary language. Because few patients will have Spanish as their primary language, we will make an *a-priori* decision to use an exact binary logistic regression model to compare the two treatment groups among Spanish speaking participants. Subsequently, a Breslow-day test may be used to compare the stratified English and Spanish speaking odds ratios for homogeneity.

A binary logistic regression model will also be used to estimate the odds of being discharged from PFPT as a function of the number of completed visits, and a Kaplan-Meier curve will be used to estimate the probability of not attending a PFPT visit following date of referral for those in the experimental and control cohorts. Using this approach, elapsed time will be measured in days from referral date to date of first visit for those who attended PFPT. Individuals who never attended PFPT will be censored at the last date they were known to be absent from therapy.

For each patient, the change in UDI-6 will be calculated by subtracting the post-treatment score from her pre-treatment score, and an independent samples *t*-test will be used to compare this change score between those assigned to the experimental group versus control group. In this model, normality and influential outliers will be assessed using QQ plots and box plots, respectively. A non-parametric Wilcoxon rank-sum test may be used if the data violate parametric assumptions. Finally, though a Kaplan-Meier method is primarily used to compare days from date of referral to date of first visit between the experimental and control groups, a Wilcoxon rank-sum test will also be used to make this comparison as a sensitivity analysis among those who attend PFPT. All analyses will be completed using SAS version 9.4 (Cary, NC).

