## **1. Protocol Synopsis**

### **1.1. Study Premise**

Pelvic floor physical therapy (PFPT) is a widely accepted treatment for many urogynecologic diagnoses, such as stress and urge urinary incontinence, pelvic organ prolapse, and myofascial pain of the levator ani muscles. This conservative treatment modality has virtually no risk, unlike medications or surgery. It is especially useful for patients who are otherwise poor surgical candidates. This treatment consists of weekly one hour long physical therapy sessions with therapists specially trained in the pelvic floor musculature. Treatment length depends on severity of symptoms and patient progress, but is usually anywhere from five to fifteen visits at our practice.

Many investigators worldwide have studied what factors influence patient compliance with this therapy. Some barriers that have been identified including being too busy with work, being afraid of vaginal palpation, feeling ashamed, feeling too old to engage in such therapy, or having symptoms that are minor. Another analysis found that age, distance from home, and diagnosis necessitating PFPT were factors in compliance. We have recently performed an IRB-approved retrospective chart review to determine PFPT compliance within our practice. We found that 66% of patients attended at least one therapy session. Of these women, 73% attended at least half of the recommended visits.

Our practice wants to develop an educational tool to improve PFPT compliance. We designed and created a four minute patient education video with assistance of the marketing department. This video includes physicians, pelvic floor physical therapists, and one of our patients speaking to the most common questions and concerns patients have. Now we aim to assess if patients who use this education tool will have improved compliance to therapy.

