#### **1.4. Summary of Study Design**

**Study Design:** Randomized controlled trial

**Population:** Clinic-based patients seen at the Loyola University Medical Center Urogynecology outpatient clinic who have been prescribed PFPT as a treatment for their condition and agree to such therapy.

**Control group:** Will read standard PFPT handout (see Appendix 4.1)

**Intervention group:** Will read standard PFPT handout plus watch education video (see Appendix 4.2)

**Study Length:** At least three months after the initial PFPT referral for each patient, medical record review will be performed to record therapy attendance, including date of first visit, number of visits recommended by the therapist, number of completed visits, and whether the patient was discharged from PFPT.

**Power-calculation:** One goal of the proposed study is to test the null hypothesis that the rate of women attending at least half of their required PT visits is identical in the two populations: Those assigned to handout only and those assigned to handout and video intervention. With proposed sample sizes of 96 assigned to handout only and 96 assigned to handout and video intervention, the study will have power of 80% to yield a statistically significant result.

This computation assumes that the difference in proportions of compliance is 20% (specifically, 70% versus 50% compliance for the intervention and control groups, respectively). It also assumes that the criterion for significance (alpha) will be set at 0.05 and that the test will be 2-tailed, meaning an effect in either direction will be interpreted.

This effect was selected as the smallest effect that would be important to detect, in the sense that any smaller effect would not be of clinical or substantive significance. It is also assumed that this effect size is reasonable, in the sense that an effect of this magnitude may be anticipated in this research.

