#### **4.3. Patient information collected (in clinic)**

Circle one:      Control      Intervention (video)

Age \_\_\_\_\_      Vaginal Parity \_\_\_\_\_      BMI \_\_\_\_\_

Insurance type:      Private      Government sponsored      Combined      Other

Race      Caucasian      Black      Asian      Eastern European      Hispanic      Other

Urogynecologic diagnoses (circle):      SUI      UUI      MUI      Urgency-frequency Syndrome

Weak pelvic floor      Defecatory dysfunction      POP      Myofascial pain      Other

Stage of Prolapse      0      1      2      3      4      Not Assessed

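### The model for completing half of the visits is valid and reaches 80% power, but leaves out age and diagnosis, which are recorded; pre-specified adjustment would add about 0 to 4 points of power under assumed prognostic strength

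*Combined protocol and SAP*

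**What the plan says.** Section 2.6 gives the method for the binary outcomes: "Binary logistic regression will be used to compare the odds of PFPT initiation, PFPT discharge, completion of half of the recommended visits". The comparison is between assigned groups, and no covariate is listed. The only baseline factor used anywhere in 2.6 is language, where the plan will "stratify the comparison of PFPT initiation by participants' primary language". For small counts, "exact logistic regression models will be used when these values are sparse".

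Section 1.1 reports that an outside analysis found that "age, distance from home, and diagnosis necessitating PFPT were factors in compliance". It gives no effect sizes. Form 4.3, completed in clinic, records age and has an item beginning "Urogynecologic diagnoses (circle" that offers nine diagnosis options. Distance from home is on neither data form (4.3 or 4.5).

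Section 1.4 powers one outcome, attendance at half or more of the visits: 96 women per arm, 70% versus 50%, two-sided alpha 0.05, power 80%. Section 2.4 specifies 1:1 block randomisation and names no stratification factor.

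**The concern.** The protocol itself cites three factors linked to compliance and collects two of them at enrolment, but its main comparison ignores both. In a randomised trial this does not bias the comparison. It does leave unexplained variation that a pre-specified model could remove.

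The sample size has little slack and no allowance for losses, so a small gain from data already in hand is worth considering. The choice has to be made before outcomes are seen, because covariates picked afterwards carry little weight.

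**Working it through.** **1. Reproduce the planned size.** Inputs from section 1.4: p0 = 0.50, p1 = 0.70, two-sided alpha 0.05, power 80%. For the Wald test of the log odds ratio, the number per arm is

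(1.960 + 0.842)² × (1/[0.5×0.5] + 1/[0.7×0.3]) / (ln 2.333)² = 7.849 × 8.762 / 0.718 = 95.8, so 96.

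This matches the plan. The pooled two-proportion formula gives 93. Exact enumeration of the Wald test at 96 per arm gives 80.7% power. Its exact type I error is 5.1%, 4.7% and 4.9% at common rates of 50%, 60% and 70%. The unadjusted model is therefore valid and delivers what section 1.4 states.

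**2. The condition behind that figure.** All 192 women must be analysed, with never-attenders counted as not completing half. The chart review in section 1.1 fits this: 66% attended at least once, and "Of these women, 73% attended at least half of the recommended visits", so 0.66 × 0.73 = 48% of all women referred, close to the 50% assumed for controls.

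**3. Gain from adjustment.** Prognostic strength is not in the documents, so it is assumed and varied. Simulated trials had 96 per arm, with 20,000 trials per setting. Age was standard normal, and three diagnosis groups had assumed shares of 50/30/20%. Log-odds ran from 0 to 0.6 per SD of age, with the same value, plus and minus, for two diagnosis groups. Marginal rates were held at 50% and 70%. The Wald test of arm was run unadjusted, and adjusted for linear age and two group indicators. An uninformative grouping means that the groups in the model are unrelated to the true ones.

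| Control-arm AUC | Correct grouping: unadjusted / adjusted power (%) | Gain (points) | Uninformative grouping: unadjusted / adjusted power (%) | Gain (points) |
|---|---|---|---|---|
| 0.50 | 80.9 / 81.1 | 0.2 | 81.0 / 81.1 | 0.1 |
| 0.57 | 79.9 / 80.8 | 0.9 | 81.0 / 81.7 | 0.7 |
| 0.60 | 80.7 / 82.0 | 1.3 | 80.8 / 81.8 | 1.0 |
| 0.63 | 80.6 / 82.9 | 2.3 | 80.8 / 82.4 | 1.6 |
| 0.66 | 81.0 / 84.2 | 3.2 | 80.8 / 82.9 | 2.1 |
| 0.69 | 81.0 / 85.1 | 4.1 | 80.7 / 83.6 | 2.9 |

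Gains are differences of the rounded figures. Monte Carlo error is about 0.3 points per power. Type I error was 5.0–5.4% both with and without adjustment. With an uninformative grouping and a mis-shaped age effect, the gain was 0.7 to 2.1 points (step) or 0.3 (U-shape), with no loss.

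**4. Cross-check by another route.** Likelihood-ratio tests were run with other covariate sets, 10,000 trials per setting, indexed by the share of outcome variance explained (R²). The gain was -0.1 to 0.4 points at R² 0, 2.2 to 2.7 at 0.056, 3.6 to 4.9 at 0.10 and 5.1 to 6.4 at 0.15. The approximation n/(1 − R²) agrees: 96/0.90 = 106.7 per arm gives 85.2%, against 81.2% at R² 0 by the same formula. With eight diagnosis indicators, type I error was 5.6% and the gain tended to be slightly smaller, which favours a small grouping.

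**5. Effect on the estimates.** The median odds ratio was 2.35 unadjusted and 2.38–2.63 adjusted. The 95% confidence interval of the standardised risk difference (influence-function standard error) covered 94.0–94.7%. Monte Carlo error on coverage is √(0.95 × 0.05/20,000) = 0.15 points, so the low end is a real, though small, shortfall.

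**The case against.** The strongest reply is that nothing is wrong. The unadjusted test is valid, reaches its stated power, and suits a design with no stratification factors. The benefit rests on one sentence about an outside analysis without effect sizes, and the assumed range starts at zero. Form 4.3 does not mark which diagnosis prompted the referral, whereas the cited factor is the diagnosis that led to therapy. Any grouping is therefore the analyst's construction.

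Most of this stands, and it limits the point to an efficiency suggestion of assumed size. It does not remove the point: age and diagnosis are already collected, and the simulations show no detectable loss when the covariates carry no information. Age alone, which needs no grouping, yields about 0 to 3 points.

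Three stronger readings are tempting, and the documents do not support them:

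- **The trial is underpowered or its main test is biased.** Steps 1 and 2 of the working show otherwise.
- **Power collapses because only attenders can be analysed.** Section 1.4 takes the denominator from the "number of visits recommended by the therapist", which a never-attender may not have. But 1.4 and 2.6 compare women by assigned group, and 2.6 restricts to attenders explicitly only for the Wilcoxon sensitivity analysis. Nor do 50% and 70% describe attenders, whose documented rate is 73%. With 0.66 × 96 ≈ 63 per arm, exact power is 37% for 73% versus 85% and 86% for 73% versus 93%, so no single figure for a loss follows. An explicit rule for never-attenders is a separate matter of endpoint definition.
- **The same gain applies to initiation and discharge.** Section 1.4 does not power these outcomes, and no discharge rate is given.

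**Conclusion.** The point holds as an optional improvement to consider. The model in 2.6 for completing half of the visits is sound as written, but it forgoes recorded baseline information that the protocol itself links to compliance.

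The gain is about 0 to 4 points if the control-arm AUC lies between 0.50 and 0.69. Four points is not a ceiling, since stronger covariates would give more. The result rests on the assumed prognostic strength and group shares, and on the all-randomised analysis with never-attenders counted as not completing half. Confidence in the direction is good; confidence in the size is only moderate.

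**What to change.** In 2.6, pre-specify that the logistic model for completing at least half of the recommended visits includes arm, age (linear) and one small diagnosis grouping.

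- **Grouping.** Several diagnoses may be circled, so write down, before outcome data are seen, a hierarchy that puts each woman in one group. As an illustration only: any myofascial pain; otherwise any of SUI, UUI, MUI or urgency-frequency; otherwise all others. If no grouping can be agreed, adjust for age alone.
- **Missing covariates.** State a simple rule, for example overall mean for age and the residual group for diagnosis.
- **Reporting.** Name the adjusted odds ratio and its test as the primary result. Give the standardised risk difference with 95% confidence interval and the unadjusted odds ratio as supporting results.
- **Unchanged.** The language-stratified analysis of initiation, the exact model for Spanish speakers and the Breslow-Day test stay as written. So does the sparse-data fallback: at the planning rates, about 96 × (0.50 + 0.30)/2 = 38.4 women per arm are expected not to complete half, so it should not be triggered for this outcome.

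**Cost.** SAP wording and a short coding rule, with no new data collection. The adjusted odds ratio is conditional on the covariates and differs somewhat from the unadjusted one. The documents do not validate the diagnosis grouping. The risk-difference interval covers slightly below 95%.

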### **1.3. Study Objectives and Hypotheses**

Objective: To determine the impact on PFPT compliance in patients who view an educational compared to standard counseling

Hypothesis: Compared to patients receiving standard counseling, those who receive both the standard counseling and educational video intervention will

- 1) Be more likely to complete at least half of their recommended PT visits
- 2) Be more likely to initiate PFPT
- 3) Will have a shorter time to initiation of PFPT
- 4) Be more likely to discharge from PFPT
- 5) Will have greater improvement in urogenital distress following PFPT

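### Hypothesis 5 (UDI-6) is tested by an unadjusted t-test on change scores, which is generally less precise than ANCOVA on the same two scores; any attenders-only result should be labelled as a post-randomisation subset.

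*Combined protocol and SAP*

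**What the plan says.** Section 1.3 lists five hypotheses. The fifth is that the video group "Will have greater improvement in urogenital distress following PFPT". Section 2.6 gives the only analysis of it: "For each patient, the change in UDI-6 will be calculated by subtracting the post-treatment score from her pre-treatment score". An independent-samples t-test "will be used to compare this change score between those assigned to the experimental group versus control group". The fallback is optional: "A non-parametric Wilcoxon rank-sum test may be used if the data violate parametric assumptions". Neither test includes the pre-treatment score as a covariate.

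Section 2.6 does not name the set of women in the UDI-6 comparison. It does name one for time to first visit, where "a Wilcoxon rank-sum test will also be used to make this comparison as a sensitivity analysis among those who attend PFPT".

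Two other places bear on this. In section 1.1, the practice's own chart review reports: "We found that 66% of patients attended at least one therapy session". In section 1.4, the only power calculation is set up to "test the null hypothesis that the rate of women attending at least half of their required PT visits is identical"; it does not concern UDI-6.

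**The concern.** There are two separate issues.

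**Precision.** A change score fixes the coefficient of the pre-treatment score at 1. ANCOVA estimates that coefficient from the data. Unless the true slope of post on pre is close to 1, the change score carries avoidable noise. The pre-treatment score is needed to compute the change anyway, so the plan already depends on the information it leaves unused. Hypothesis 5 has no sample-size justification, so it has little precision to spare.

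**Who is scored.** The hypothesis concerns improvement after therapy, and the second score is called post-treatment. Women who never start therapy may therefore have no second score. Hypothesis 2 says the video should raise the proportion who start. If only attenders are scored, randomisation no longer protects the comparison: the video arm may include women who would not have started under the handout alone. The result would not be the effect of the video in all randomised women. The plan does not say that the analysis is limited to attenders; it leaves the question open.

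**Working it through.** **The plan's own figure.** Section 1.4 gives 96 per arm for 80% power, at 70% versus 50% and two-sided alpha 0.05. For a Wald test on the log odds ratio, which matches the planned logistic regression:
- log odds ratio = log(0.7/0.3) = 0.847
- variance = 1/(96 × 0.25) + 1/(96 × 0.21) = 0.0913, so SE = 0.302
- 0.847/0.302 − 1.96 = 0.845, so power is 80.1%

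The figure reproduces and does not involve UDI-6.

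**Precision: inputs.** N = 192 (96 per arm) is from section 1.4. The pre-post correlation r and the post/pre SD ratio k are not in the documents. I assume r = 0.3 to 0.8 and k = 0.8, 1 and 1.2.

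**Formulas**, with the pre-treatment SD set to 1:
- change-score variance = k² + 1 − 2rk
- ANCOVA variance = k²(1 − r²)
- difference = (1 − rk)², which is never negative and is zero only when the slope rk is 1
- cost of estimating the covariate: multiply the ANCOVA variance by 1 + 1/(N − 4), which is 1.0053 at N = 192 and 1.0081 at N = 127

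**Variance ratio, ANCOVA/change, N = 192, cost included**

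| k | r = 0.3 | r = 0.5 | r = 0.7 | r = 0.8 |
|---|---|---|---|---|
| 0.8 | 0.505 | 0.574 | 0.631 | 0.643 |
| 1 | 0.653 | 0.754 | 0.855 | 0.905 |
| 1.2 | 0.766 | 0.876 | 0.971 | 1.002 |

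At k = 1 the confidence interval is narrower by 1 − √ratio: 19%, 13%, 8% and 5%.

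**Detectable difference and power at k = 1.** SE = √(variance × 4/N). At r = 0.3 the SE is √(1.4 × 4/192) = 0.171 for the change score and √(0.91 × 1.0053 × 4/192) = 0.138 for ANCOVA. Using the t distribution, in pre-treatment SDs:

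| r | Detectable at 80% power: change | Detectable at 80% power: ANCOVA | Power of change t-test at the ANCOVA difference |
|---|---|---|---|
| 0.3 | 0.481 | 0.389 | 62% |
| 0.5 | 0.406 | 0.353 | 68% |
| 0.7 | 0.315 | 0.291 | 74% |
| 0.8 | 0.257 | 0.245 | 76% |

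**Where ANCOVA loses.** At N = 192 this needs a slope of 0.946 to 1.043 (k = 1.2) or above 0.989 (k = 1). It never happens at k = 0.8. The worst loss is 1/188 = 0.5% of variance. If only 66% are scored (0.66 × 192 = 127), it is 1/123 = 0.8%. Simulation of 40,000 trials at N = 127 agrees: ratios of 0.654, 0.757 and 0.907 for k = 1 and r = 0.3, 0.5 and 0.8, and 1.005 for k = 1.2 and r = 0.8.

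**Selection, as illustration only.** Take 66% starting in the control arm (section 1.1), or 0.66 × 96 = 63 women. Assume the video raises starting to a proportion p and stops no one from starting. Extra starters are then (p − 0.66)/p of the video-arm attenders. Assume also that their expected change differs from that of other attenders by 0.25 or 0.5 SD, while the video affects no woman's score:

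| p | Share of extra starters | Shift at 0.25 SD | Shift at 0.5 SD |
|---|---|---|---|
| 71% | 7.0% | 0.018 | 0.035 |
| 76% | 13.2% | 0.033 | 0.066 |
| 86% | 23.3% | 0.058 | 0.116 |

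A separate simulation assumed 66% versus 80% attendance, a correlation of 0.4 between propensity to attend and change, and no video effect on the score. The difference among attenders was −0.08 SD; among all randomised women it was 0.00.

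**The case against.** The planned test is valid, prespecified, compared by assigned arm and backed by diagnostics. A change score also answers the hypothesis as worded. UDI-6 is the last of five hypotheses and is not powered. The gain depends on r and k, which nobody can read from the documents; at r = 0.8 with equal SDs the detectable difference only moves from 0.26 to 0.25 SD. All of this is true. It makes the point one of efficiency, and the size must be read as a range. It does not make the change score preferable, because the possible loss from ANCOVA is under 1% of variance.

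A sharper objection is that the precision argument needs a pre-treatment score that randomisation balances. In an attenders-only set, or with a pre-treatment score taken after randomisation, the arms may differ on it. The two methods then differ in expectation by (1 − slope) × imbalance: an assumed 0.1 SD imbalance and slope of 0.5 give 0.05 SD. This stands as a limit on the precision figures, which apply to the all-randomised comparison. It does not favour the change score, which uses the same two scores and is no less exposed.

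It is also fair that section 2.6 speaks of each patient and nowhere limits UDI-6 to attenders. The labelling point is therefore conditional.

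**Conclusion.** The concern holds. If all randomised women have both scores, and the first is unaffected by randomisation, the planned t-test generally gives a wider interval than ANCOVA. With equal SDs and an assumed r of 0.3 to 0.8, ANCOVA cuts variance by 35% to 10%. With k = 0.8 the cut is 50% to 36%. With k = 1.2 it runs from 23% to a 0.2% loss.

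If only attenders are scored, the estimate is not the effect of the video in all randomised women, whichever method is used. An assumed range of inputs puts the possible shift at 0.02 to 0.12 SD.

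The change should be made, but it does not touch the powered attendance endpoint. The algebra is certain; the size in this trial is not, because r, k and the UDI-6 SD are not given.

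**What to change.** In section 2.6, make the hypothesis 5 analysis an ANCOVA of post-treatment UDI-6 on arm and pre-treatment UDI-6, reporting the adjusted difference with a 95% confidence interval. Keep the rank-sum test on the change score as a prespecified sensitivity check, run whatever the diagnostics show, so that the choice of test does not depend on the data.

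Name the UDI-6 analysis set. If scores come only from attenders, report the number scored by arm and describe the result as a comparison in a post-randomisation subset, not as the effect of the video in all randomised women. It would help to state the source and timing of both scores in the same place.

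The cost is SAP wording and one degree of freedom. No new data collection or patient contact is needed.

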#### 4.4 Patient questionnaire

Do you have any further questions? No/Yes \_\_\_\_\_

1) After your visit today, how **well informed** do you feel about the role of pelvic floor physical therapy in treating pelvic floor symptoms?

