## Too much information

#### **4.5 Patient information collected (from EMR < nine months later)**

**Time to first PFPT visit from day of referral:** \_\_\_\_\_ days

**Physician who referred:**      [name]      [name]      [name]      [name]

**Number of recommended visits:** \_\_\_\_\_

**Number of completed visits:** \_\_\_\_\_

**Discharged from PFPT practice (circle):** yes      no

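### Hypothesis 5 plans a between-arm test of UDI-6 change, but no visible form collects UDI-6, neither score has a date, and never-starters have no post-treatment score

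*Combined protocol and SAP*

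**What the plan says.** The fifth hypothesis in section 1.3 is that women shown the video "Will have greater improvement in urogenital distress following PFPT". It names no instrument and no time point.

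Section 2.6 supplies the instrument. For every patient, "the change in UDI-6 will be calculated by subtracting the post-treatment score from her pre-treatment score". The arms, as assigned, are then compared on this score with a two-sample t-test. A Wilcoxon rank-sum test may replace the t-test if its assumptions fail. Section 2.6 gives no window for either score and no rule for women without one.

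The data-collection sections do not mention UDI-6:

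- **Section 2, enrolment visit:** further questions are recorded and "The patient will also fill out a visual analog scale about how informed she feels".
- **Section 2, follow-up:** the chart is monitored for time to attendance and for compliance. No later contact with the patient is planned.
- **Section 1.4, Study Length:** the plan for the chart review, at least three months after referral, reads in part: "medical record review will be performed to record therapy attendance, including date of first visit, number of visits recommended by the therapist, number of completed". The list ends with discharge status.
- **Appendix 4.3, in-clinic form:** arm, age, parity, BMI, insurance, race, diagnoses and prolapse stage.
- **Appendix 4.4, questionnaire:** an item asking "Do you have any further questions", then three ratings of the counselling.
- **Appendix 4.5, chart form (under nine months later):** days to first visit, referring physician, recommended visits, completed visits and discharge.

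**The concern.** Hypothesis 5 has a test but no data source. If the forms are followed as they stand, there is nothing to analyse. If the gap is filled from whatever the chart holds, the post-treatment scores can come only from women who had treatment.

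That subset is formed after randomisation, by behaviour that hypotheses 1 to 4 say the video changes: starting, reaching half the visits, starting sooner and being discharged. If the video draws in women who would otherwise have stayed away, the scored women in the two arms differ in kind. A difference in their mean UDI-6 change could then reflect who attended rather than any symptom benefit, and the more the video affects attendance, the less comparable the groups become.

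Section 2.6 deals with this problem for another outcome. In the time-to-first-visit analysis, never-attenders are censored, and the attender-only rank-sum test is a sensitivity analysis. UDI-6 has no equivalent provision.

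**Working it through.** **1. The plan's own figure.** The only sample-size figure is for compliance: 96 per arm, 70% v 50%, two-sided alpha 0.05, power 80% (section 1.4). A Wald test on the log odds ratio, which matches the planned logistic regression, gives

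n = (1.960 + 0.842)² × (1/0.21 + 1/0.25) / [ln(0.7/0.3)]² = 95.8, so 96 per arm.

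The usual two-proportion formula gives 81.2% power at 96 per arm. The figure reproduces. It does not involve UDI-6, for which the documents state no SD, effect or power.

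**2. Does a post-treatment score exist at chart review?** Section 1.1 describes weekly sessions, usually five to fifteen. The fifteenth weekly visit falls 14 weeks after the first. Section 1.4 allows chart review from three months after referral, about 13 weeks. A woman on a long course can still be in treatment when reviewed, even if she started on the day of referral. A woman who never starts has no post-treatment time at all.

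**3. How many women could lack a score?** The documents do not say what attendance produces a score, so two assumed conditions are shown, each under two sets of rates, with 96 women per arm.

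| Score assumed to require | Rates (control v video) | With score | Without, of 192 |
|---|---|---|---|
| Starting therapy | 66% v 66% (section 1.1, both arms) | 192 × 0.66 = 127 | 65 (34%) |
| Starting therapy | 66% v 80% (80% assumed) | 63.4 + 76.8 = 140 | 52 (27%) |
| Half the visits | 50% v 70% (section 1.4) | 48 + 67.2 = 115 | 77 (40%) |
| Half the visits | 66% × 73% = 48.2% in both arms (section 1.1) | 192 × 0.482 = 93 | 99 (52%) |

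In the third row the t-test would compare about 48 women with about 67.

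**4. Precision.** The detectable difference at 80% power is (1.960 + 0.842) × √(1/n₁ + 1/n₂), in SD units:

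- all 192 scored: 0.40
- 127 scored, equal arms: 0.50
- 48 v 67: 0.53
- 93 scored, equal arms: 0.58

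Without a UDI-6 SD these cannot be turned into points.

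**5. Direction of bias.** Assume that 66% v 80% attend, that women who would attend in either arm improve 20 points, that the extra 14% drawn in by the video improve x points, and that non-attenders improve 0. All of these values except the 66% are assumptions.

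- Attender-only difference = (0.66 × 20 + 0.14x)/0.80 − 20
- All-randomised difference = (0.66 × 20 + 0.14x) − 0.66 × 20 = 0.14x

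| x | Attender-only | All randomised |
|---|---|---|
| 10 | 14.6/0.80 − 20 = −1.75 | +1.4 |
| 20 | 16.0/0.80 − 20 = 0 | +2.8 |
| 30 | 17.4/0.80 − 20 = +1.75 | +4.2 |

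The attender-only result can be negative, zero or positive while the all-randomised effect is positive throughout. Its sign depends on how the extra attenders compare with the others, which the documents do not tell us.

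**The case against.** The strongest reply is that hypothesis 5 speaks of improvement after PFPT, so it may concern treated women only, and that UDI-6 is the last of five hypotheses and not the powered outcome. The second part stands and limits the weight of the point. The first does not rescue the plan: a comparison among treated women is not protected by randomisation, and section 2.6 promises the change score for every patient.

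A reader might go further than the documents allow in four ways.

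- *The trial cannot answer its stated objective.* The research question (section 1.2) and the objective (section 1.3) concern compliance. Neither they nor the compliance analyses depend on UDI-6.
- *At most 127 women could have a score.* The 66% is a historical rate without the video, so 127 is not a ceiling. With 80% starting in the video arm the number is about 140.
- *The test would turn a benefit into apparent harm.* That needs the extra attenders to improve less than the others. At equal improvement the attender-only difference is 0, and at greater improvement it is positive. It is also a different quantity from the all-randomised effect.
- *Routine chart scores will be used.* No section says that UDI-6 is charted routinely. The text shows only that its source, dates and analysis set are unspecified.

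Two further cautions hold. Appendix 4.2 was not in the text available; section 1.4 cites it for the video, so a UDI-6 form there is unlikely but cannot be excluded. Trial participants have agreed to PFPT, so more than 66% may start. That would narrow the gap without supplying a score or a date.

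**Conclusion.** The point holds as a defect in a secondary, non-powered hypothesis. In the available text no step collects UDI-6, neither score is dated, and no rule covers women who never start. Followed as written, the plan gives either no data or a comparison within a subset selected by attendance.

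The missing share is about 27% to 34% if a score requires starting, and about 40% to 52% if it requires half the visits. Both conditions, and the 80% rate, are assumptions; the other rates are the plan's own. The direction of bias is unknown. The defect itself rests on the text and not on these figures. It should be corrected because section 2.7 foresees a new counselling standard from these findings, and a symptom-benefit claim should not rest on an undefined subset.

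**What to change.** Amend the protocol as follows:

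1. Add UDI-6 to the in-clinic form (4.3), completed before randomisation. The form also records the arm, so the order must be stated.
2. Repeat UDI-6 once, by mail, phone or portal, at a fixed time from referral, for every randomised woman whether or not she attended.
3. Abstract the compliance data only up to a date no later than that contact. A symptom questionnaire could prompt a woman to attend, and this cut-off keeps it from altering the compliance outcome.
4. In section 2.6, define the hypothesis 5 outcome as change from enrolment to that date in all randomised women, and state how missing scores are handled.

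The cost is one short questionnaire at enrolment and one remote contact per woman, about 192 in a trial that planned none, with some non-response. The estimand also changes, from improvement after PFPT to improvement in all randomised women, so hypothesis 5 must be reworded to match.

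If the sponsor will not collect UDI-6, remove hypothesis 5 as a comparative hypothesis, add a UDI-6 field to form 4.5, and report chart scores among attenders descriptively only. This needs no patient contact, but it gives up any claim that the video improves symptoms.
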